APPENDIX

1. Amendments to the Protocol	12
2. Amendments to the Statistical Analysis Plan	13

PROTOCOL Version 1.3 (See Table of Amendments)

Multi-Center Randomized Controlled Trial of Refeeding in Anorexia Nervosa

1. Introduction

Current recommendations to guide the clinical care of AN patients hospitalized with medical instability due to malnutrition are based solely on retrospective or observational studies and/or clinical experience. No studies to date have prospectively tested high calorie refeeding (HCR) and the long-term impact on recovery is unknown. Consensus has developed over recent decades that patient safety can only be guaranteed using low calorie refeeding (LCR). The entrenchment of clinical practice without supporting evidence is a widely recognized dilemma in healthcare. While RCTs are considered the “gold standard” to establish evidence-based medicine, until recently there was insufficient data to propose such a study of refeeding in AN. We now have preliminary findings to indicate that LCR might be too cautious and that HCR appears feasible and may improve long-term recovery. Thus, we are poised to compare these two treatments in a parallel, randomized fashion.

2. Study Design

The purpose of this multi-center randomized controlled trial is to compare LCR vs. HCR refeeding strategies for hospitalized adolescents with AN. Participants will be recruited upon hospital admission at two centers (UCSF and Stanford) to maximize sample size, and randomly assigned 1:1 within site to one of the two strategies. A total of 120 participants age 12-24 yrs who meet DSM-5 diagnostic criteria for AN and atypical AN and present as medically unstable due to malnutrition will be enrolled. Treatments will not be blinded, since both the patients and clinicians who work with this population are highly skilled at estimating kcal and would be able to determine their group assignment by simply viewing the meal trays. In addition, target kcal will be reached faster in HCR and this would be apparent on physician orders. The proposed study is powered to detect a meaningful difference in clinical remission (Aim 1A).

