2.2. Outcomes

The primary analysis of the study adopts a modified intent-to-treat (mITT) approach to compare outcomes between randomized HCR and LCR participants who received treatment for at least one day. Patients who are ineligible post randomization, provide no assent after parent's consent, or withdraw before receiving any treatment, will not be included in the mITT analysis for reasons of data unavailability, ethics and clinical relevance. Sensitivity analyses will be conducted to check that 1) withdrawal patients are not different from patients in both groups included in mITT in baseline covariates; and 2) including withdrawal patients in the analyses will not change results and conclusion of mITT analyses. The sensitivity analyses will provide us

reassurance of mITT results.

Aim 1A: Primary (long-term) efficacy outcome. A (generalized) linear mixed-effects regression model (GLMM) will compare study arms with respect to achievement and maintenance of clinical remission. Clinical remission is defined as the combination of mBMI and EDE-Q score at mo 1,3,6,12 (separate analyses below) and measured at 1, 3, 6, and 12 months as 1) clinically remitted (yes or no) and 2) weight recovered (percent of mBMI). The models will include time, treatment group, time*treatment group interaction, and unbalanced baseline covariates if any as fixed effects, while sites and patients will be included as random effects to account for the correlation due to clustering. The time*treatment group interaction provides mITT effect of HCR compared to LCR on clinical remission over time. The average remission rates and scores and their 95% confidence intervals (CIs) will be estimated from the model. GLMM accounts for the fluctuating nature of mBMI and EDE-Q in AN and uses all available data with missing at random assumption, instead of a stronger assumption of missing completely at random required in other models. Aim 1 models will be supplemented with secondary analyses: (i) potential moderators at baseline (included in regression models as main effects and interactions with period and time), may include DSM-5 criteria and EDE-Q thresholds of risk and (ii) potential mediators at follow-up (included as time-dependent covariates), may include food recall (DDS and DVS), healthcare utilization, or incidence of AEs. In addition, separate mixed-effects models will analyze continuous versions of mBMI and EDE-Q to describe longitudinal trajectories.

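### The Aim 1A moderator analysis names an undefined *period* term and no moderator-by-treatment-group term, so as written it tests prognosis rather than effect modification

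*Combined protocol and SAP*

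**What the plan says.** SAP section 2.2 sets out the Aim 1A mixed model: "The models will include time, treatment group, time*treatment group interaction, and unbalanced baseline covariates if any as fixed effects". Remission is "measured at 1, 3, 6, and 12 months". The treatment effect is tied to one term: "The time*treatment group interaction provides mITT effect of HCR compared to LCR on clinical remission over time".

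Two secondary analyses are then added. The first takes possible baseline moderators and enters them as "main effects and interactions with period and time"; DSM-5 criteria and EDE-Q risk thresholds are given as possible examples. The second concerns "potential mediators at follow-up (included as time-dependent covariates"; food-recall scores, healthcare utilisation and incidence of AEs are given as possible examples. Nothing further is said about the form of either model.

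**The concern.** Moderation of a treatment effect means that the effect differs between levels of a baseline variable. That requires a term containing both the moderator and the arm, and the moderator sentence names none. The paragraph has a term for the randomised factor (*treatment group*) and uses it consistently, but this sentence uses *period*, which appears nowhere else in the Aim 1A specification.

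An analyst following the text would report a moderator × time coefficient as moderation. That coefficient can be large when HCR and LCR work equally well in every subgroup, and null when they do not. If the term is instead settled during analysis, the choice of interaction is made with the data in hand.

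The mediator sentence raises a smaller question. Adding a post-randomisation variable to the model changes the arm coefficient for several reasons, of which mediation is only one.

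**Working it through.** **1. The plan's own figure.** The SAP gives no figure for either secondary analysis. Its Aim 1A figure (section 2.3) is 80% power, two-sided 0.05, 60 per arm, 8% vs 28%. With pooled variance: mean rate 0.18; null SE = √(2 × 0.18 × 0.82/60) = 0.0701; alternative SE = √((0.08 × 0.92 + 0.28 × 0.72)/60) = 0.0677; power = Φ((0.20 − 1.96 × 0.0701)/0.0677) = 82.2%. An HCR rate of 27% gives 78.9%, so 28% is the smallest whole-percent rate reaching 80%. The figure is sound, and its inputs are reused in step 5.

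**2. What the stated terms estimate.** Let A be arm, T time and M the moderator. The base model plus the named terms, on the model's own scale, is

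b0 + b1·T + b2·A + b3·A·T + b4·M + b5·M·T.

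The arm effect at time t is b2 + b3·t, which does not contain M. The model therefore holds the arm effect equal across moderator levels, and b5 measures prognosis over time. Adding b6·A·M + b7·A·M·T makes the arm effect differ between M = 1 and M = 0 by b6 + b7·t, which is the moderation quantity.

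**3. Can *period* supply the missing arm term?**

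- *A treatment period.* Protocol section 1 says the trial will "compare these two treatments in a parallel, randomized fashion", so there are none.
- *Hospital versus follow-up.* SAP 2.2 (Aim 3) and the SAP amendment table use the word for the hospital stay. Aim 1A remission is assessed only at months 1–12, so this factor would be constant.
- *A slip for treatment group.* This gives moderator × treatment group. Read as two separate interactions, it still lacks moderator × treatment group × time, the term that matches the SAP's own definition of the treatment effect.

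**4. Size of the difference on the literal reading.** The documents give no moderator effects, so these are assumed. The simulation used 120 participants, visits at 1, 3, 6 and 12 months, a continuous outcome with total SD 1, a moderator split of about 50/50, and 2,000 runs. Entries are rejection rates at 0.05.

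| Assumed truth | M × time (as written) | M × arm | M × arm × time |
|---|---|---|---|
| Prognostic only (M × time 0.2 per SD of visit time) | 93% | 5% | 5% |
| Arm effect differs by 1.0 SD at all visits | 5% | 89% | 5% |
| Arm-by-time slope differs by 0.4 | 4% | 6% | 93% |

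**5. Power of the corrected test.** Cross-sectional approximation: power = Φ(d/√V − 1.96), where d is the difference between the two subgroup risk differences and V sums p(1 − p)/n over the four cells. LCR is 8% in both subgroups. Inputs are 60 per arm, or 51 after 85% retention.

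- Best 20-point case (60 per arm, 50/50; 8→28% vs 8→8%): V = (0.2752 + 0.1472)/30 = 0.01408; 0.20/0.1187 − 1.96 = −0.27; power 39%.
- Worst 20-point case (51 per arm, larger-effect subgroup 30%; 8→38% vs 8→18%): V = 0.3092/15.3 + 0.2212/35.7 = 0.02640; 0.20/0.1625 − 1.96 = −0.73; power 23%.
- 40-point case (8→48% vs 8→8%): 78–89% at 60 per arm, 71–84% at 51.

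**6. Mediator timing.**

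| Candidate | When measured | Source |
|---|---|---|
| Food recall | Same week as the outcome visit | Protocol 3.2.c(2) |
| Healthcare utilisation | Interval since the previous visit | Protocol 3.2.c(3) |
| Electrolyte AEs | In hospital, before all Aim 1A outcomes | SAP 2.2, Aim 2 |

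Only food recall coincides with the outcome. Table 1 of the protocol schedules it at 10 days and at 1, 3, 6 and 12 months, so an earlier follow-up value is scheduled before every remission assessment.

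**7. Mediator-adjusted arm coefficient.** Assume a true arm effect of 0.40, an arm effect of 0.5 on a mediator that has no effect on outcome, and an unmeasured cause acting on both with strength u (all residual SDs 1). The adjusted coefficient is 0.40 − 0.5 × u²/(u² + 1). For u = 0 it is 0.40 (simulated 0.41); for u = 0.5, 0.30 (simulated 0.30); for u = 1, 0.15 (simulated 0.16). The drop would look like mediation although there is none.

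**The case against.** The strongest reply is that *period* is a slip. The moderator terms are added to a model that already holds treatment group and its interaction with time, and a statistician writing about moderators most likely meant treatment group. Alternatively, the word may be left over from when Aim 1B was a 12-month mixed model (SAP amendment 2). Either is plausible. A reader might infer that the sponsor chose to leave arm out, or that moderation cannot be examined in this trial; the documents support neither. The simulations in step 4 show what follows from the literal reading and are not evidence that it was intended. What stands is that no meaning of the word found in the documents supplies an arm interaction.

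On mediators, a reader might infer that every candidate is measured alongside the outcome and that covariate adjustment is invalid. That goes too far. Utilisation covers the preceding interval, although it may reflect earlier non-remission, and in-hospital AEs cannot be caused by later relapse. Adjustment can give a direct effect if mediator and outcome share no unadjusted causes (step 7, u = 0). Nor does the SAP say that the adjusted arm coefficient will be read as the treatment effect; it assigns that role to the base model.

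These are also secondary analyses of variables listed only as possibilities, which limits the consequences.

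**Conclusion.** The point holds for moderators as a specification defect: an undefined term stands where a treatment-group interaction is needed, and the stated terms test prognosis over time. On the literal reading the stated term has no more than its nominal error rate against true moderation (4–5% in step 4), and 93% rejection when the moderator is only prognostic. Those figures depend on assumed effects and a continuous outcome.

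The corrected test would be weak: 23–39% power for a 20-point difference between subgroup effects. That range rests on assumed subgroup rates and splits and ignores any gain from repeated visits.

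For mediators the defect is under-specification. No indirect-effect estimand, arm-to-mediator model or confounder set is given, although protocol 3.2.c(3) itself names psychotherapy modality and adherence as possibly prognostic. The size of any bias cannot be derived from the documents. The primary arm comparison, the safety comparison and the sample size are untouched.

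**What to change.** - **Moderators.** Replace the reference to *period* and time with moderator × treatment group and moderator × treatment group × time, keeping all lower-order terms. State which of the two is the test of moderation; the three-way term matches the SAP's definition of the treatment effect. Label the analysis exploratory and report interaction estimates with confidence intervals.
- **Mediators.** For each candidate, state its timing, the indirect-effect estimand, the model for arm on mediator and the mediator–outcome confounders adjusted for. Lag food recall to the previous scheduled visit (10 days for month 1, month 1 for month 3, and so on). Utilisation and in-hospital AEs need no lag, but acknowledge that utilisation may follow from earlier non-remission. State that the mediator-adjusted arm coefficient is not reported as the treatment effect.

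The moderator change costs a sentence of SAP text. The mediator change costs a short paragraph and some extra modelling. Neither needs new data collection, and the lag loses no outcome visit by design, because the 10-day recall is already scheduled.

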2.2. Randomization

Participants will be stratified by site and randomly assigned 1:1 to the two intervention strategies within 24 hr of hospital admission. The Data Coordination Center (DCC) will provide a secure unpredictable allocation sequence (e.g. A B B A ...) which will be programmed into a secure electronic study tracking system for assignment of each accrued participant. The sequences will be generated using block size of two to four to maximize balance between arms throughout accrual while ensuring the sequences remain unpredictable. As patients consent to study participation, clinical-research staff will assign the next available study ID number in sequence, identify the allocated intervention arm, and inform participants and their families of the assignment. In turn, the clinical research staff will provide the linked study ID number and Medical Record Number to the DCC, which will store this Personal Health Information in a HIPAA-compliant manner along with the intervention assignment.

3. Study Procedures

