2.1. Pool of participants

a. Projected pool of eligible participants and accrual rate: At Stanford, in 2012 there were 295 admissions to the dedicated inpatient eating disorders unit, with approximately 36% of patients meeting DSM-4 criteria for AN; 100 similar patients were admitted at UCSF. With the broader eligibility criteria also including DSM-5, we anticipate at least 40% of patients (120 per yr at Stanford and 40 at UCSF) will be eligible. Of those who are eligible, we estimate that at least 50% will agree to participate and thus we will not attempt to achieve equal enrollment across sites. We will accrue 3-4 participants per mo over 3 yr until N=120 is reached and retain 85% of this sample through 12 mo as shown in open follow-up studies of participants with AN.

b. Commitments of Site PIs, Research Teams, and Participants: Both site PIs have successfully recruited and retained AN participants in research projects and seen them to completion and publication. Furthermore, co-I [name] is a faculty biostatistician with extensive experience in clinical trials. She will lead the DCC, aiming to ensure the trial is designed, executed, and analyzed without bias. Patient incentives to participate will emphasize the value of their contributions to medical research and remuneration for their time.

c. Data Analyses:

Sample Description: The study sample will be summarized and described (e.g., mean \pm SD) by stratification factor and baseline covariates to confirm general balance by arm and data will be summarized for completeness of follow-up (e.g., length of stay, last visit).

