Aim 1B: Secondary (short-term) efficacy outcome: Time to restore and maintain medical stability in hospital is defined as days to reverse the medical instability indicators for hospitalization in adolescents with eating disorders. A six-point index will adjudicate daily medical stability: 1.) 24-hour heart rate (HR) ≥ 45 bpm, 2.) systolic blood pressure (SBP) ≥ 90 mmHg, 3.) temperature $\geq 35.6^\circ$ C, 4.) orthostatic increase in HR ≤ 35 bpm, 5.) orthostatic decrease in systolic BP ≤ 20 mmHg, and 6.) $\geq 75\%$ of mBMI. Each of the six criteria were scored as "1" if met, "0" if unmet and missing (not scored) if not measured. Medical stability was considered restored when all criteria were stable for 24 hours, allowing a maximum of two missing values (i.e. participants were considered stable if meeting 4 of 4, 5 of 5 or 6 of 6 measured criteria). All randomized participants who receive at least one day of treatment, including those who withdraw at any time during the refeeding intervention, will be included in the mITT analysis. Specifically, survival analysis with log rank test will compare time to achieve medical stability by arm while accounting for the correlation within sites; participants who do not meet stability criteria by hospital discharge will be right-censored. In case of any important unbalanced covariate at baseline, Cox proportional hazard ratio model will be used to control for the potential bias due to the confounder. Additionally efficacy outcomes will include the proportion achieving medical stability in each arm, change in %mBMI as compared to baseline, and time to restore HR.

Aim 2. Safety: Primary indicator of safety will be incidence of the following electrolyte abnormalities during hospitalization: 2A) hypophosphatemia (<3 mg/dL), 2B) hypomagnesaemia (≤ 1.7 mg/dL), 2C) hypokalemia (< 3.5 mEq/L). These AEs will be tracked, recorded, reported to the DSMB for monitoring, and to the IRB and NIH as needed, according to the attached DSMP. Incidence of the electrolyte abnormalities and proportion receiving supplementation to correct electrolyte abnormalities will be compared by arm during hospitalization using Fisher's exact test. Additional safety outcomes: the proportion receiving electrolyte supplementation during the hospitalization between groups will be compared with Fisher's exact test; time to electrolyte nadir will be compared with Wilcoxon rank sum test.

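### With two sites as randomisation strata, site should be a fixed effect or stratum; the SAP treats it as random clustering in Aim 1A, leaves the Aim 1B method unnamed and omits it from the Aim 2 tests

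*Combined protocol and SAP*

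**What the plan says.** Protocol section 2 (Study Design): "Participants will be recruited upon hospital admission at two centers (UCSF and Stanford) to maximize sample size". Protocol section 2.2 (Randomization): "Participants will be stratified by site and randomly assigned 1:1 to the two intervention strategies", and "The sequences will be generated using block size of two to four". Site is therefore a randomisation stratum, with both arms present in each.

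SAP 2.1 expects 120 eligible patients a year at one site and 40 at the other, and states that "we will not attempt to achieve equal enrollment across sites".

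SAP 2.2 then handles site in three ways:

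- **Aim 1A (primary):** "sites and patients will be included as random effects to account for the correlation due to clustering".
- **Aim 1B:** a log-rank test will "compare time to achieve medical stability by arm while accounting for the correlation within sites". The technique is not named. A Cox model is the fallback if an important baseline covariate is unbalanced, and site is not mentioned there.
- **Aim 2:** Fisher's exact test for incidence and supplementation and a Wilcoxon rank sum test for time to nadir, with no site term.

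SAP 2.1.c describes the sample by stratification factor, but no test is stated to be stratified by it.

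**The concern.** Clustering methods suit many units that can be regarded as a sample from a population of units. Here there are two fixed centres, and patients are randomised inside each. Two units cannot support a useful between-unit variance, and robust variances summed over clusters rely on the number of clusters being large.

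The stakes differ by aim. In Aim 1A the site term may vanish or take an arbitrary size. In Aim 1B the wording admits procedures with very different properties, some of them unusable. In Aim 2 the cost is sensitivity, which deserves attention because the hypothesis there is that the arms will not differ.

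**Working it through.** **Inputs from the documents.** Two sites; 1:1 allocation within site; blocks of two to four; N = 120; eligible patients 120 and 40 a year. If enrolment follows eligibility, the larger site has 120 × 120/160 = 90 patients and the other 30. This split is an assumption.

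**The plan's own figure.** SAP 2.3 gives 80% power for 8% vs 28% with 60 per arm, two-sided 0.05. With pooled p = 0.18, SE = √(2 × 0.18 × 0.82/60) = 0.0701, and 0.20/0.0701 − 1.96 = 0.89, giving power 81.4%. The figure is reproduced. Site does not enter it, so nothing below puts it in doubt.

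**Aim 1A: site variance from two sites.** The estimate rests on a chi-square with 1 df.

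- 95% limits for the variance: 1/5.02 = 0.20 to about 1,018 times the estimate.
- For a simple mean, a moment estimate is zero whenever the squared standardised site difference is below 1. With no true difference this has probability P(χ²₁ < 1) = 68%.
- With 90 and 30 patients, the SE of the site difference is √(1/90 + 1/30) = 0.211 SD. A true difference of 0.2 SD still gives zero in about 50% of trials, and 0.4 SD in 18%.

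These figures use a simple mean as a stand-in for the longitudinal model.

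**Aim 1B, if implemented as a site-clustered robust variance.** Let U₁ and U₂ be the site log-rank scores, with information shares w and 1 − w.

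- *Robust score (log-rank) test:* the statistic is (U₁ + U₂)²/(U₁² + U₂²). Since (U₁ + U₂)² ≤ 2(U₁² + U₂²), it cannot exceed 2.0. The 5% critical value is 3.84, so the test never rejects. Simulation gave no rejections.
- *Robust Wald test (Cox):* at the estimate the two site residuals sum to zero, so the robust SE rests on one random quantity, independent of the estimate. The ratio z is a Cauchy variable divided by √(2w(1 − w)). Hence P(|z| > 1.96) = 1 − (2/π) arctan(1.96 √(2w(1 − w))).
  - w = 0.50: 1.96 × 0.707 = 1.386, giving 39.8%.
  - w = 0.75: 1.96 × 0.612 = 1.200, giving 44.2%.
  - A simulation of 1,000 null trials with 90 and 30 patients gave 41.2%, against 4.6% for a site-stratified and 4.4% for an unstratified analysis.

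**Aim 1B, stratified against ignoring site.** Assumed: 90/30 split, control median 9 days, uniform censoring at days 7-21, treatment hazard ratio 1.7 for power, 1,500 runs.

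| Site hazard ratio | Type I, unstratified | Type I, stratified | Power, unstratified | Power, stratified |
|---|---|---|---|---|
| 1 | 6.1% | 6.1% | 71% | 71% |
| 1.5 | 4.9% | 4.8% | 71% | 72% |
| 2 | 4.5% | 5.3% | 69% | 71% |
| 3 | 3.6% | 5.1% | 64% | 71% |

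The Monte Carlo SE for type I error is about √(0.05 × 0.95/1,500) = 0.6 points.

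**Aim 2: exact site-stratified Cochran-Mantel-Haenszel against pooled Fisher.** Assumed: 90/30 split, odds ratio 3, 6,000 runs.

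| Event rates in LCR, larger / smaller site | Power, Fisher | Power, exact stratified |
|---|---|---|
| 5% / 5% | 24.4% | 24.6% |
| 15% / 15% | 63.5% | 64.0% |
| 15% / 40% | 64.9% | 68.5% |
| 10% / 50% | 49.4% | 58.8% |

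The asymptotic version of the stratified test looks better (72% against 64% at 15% in both sites), but with equal site rates that gap is Fisher's own conservatism and not a gain from stratifying.

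**The case against.** The best defence is that little harm is certain.

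- **Aim 1A.** Allocation is 1:1 within site in small blocks, so arm is nearly orthogonal to site before exclusions and dropout. The site variance is most often zero when the sites do not differ, which is when losing it matters least. This stands: a reader might infer that the primary comparison is biased, and the documents do not support that.
- **Aim 1B.** The SAP does bring site in, and a stratified log-rank is one acceptable way to carry out its wording. A reader might infer that the stratum is ignored, or that a false-positive rate near 40% is built into the plan. Neither follows. The 40-44% belongs to a robust Wald test from a Cox model; the named test is the log-rank, whose two-cluster robust form fails the other way by never rejecting. What stands against the plan is that the wording does not choose among these.
- **Aim 2.** Pooled Fisher is valid, and the exact stratified test gains almost nothing at low incidence, which is what the SAP amendment table reports. This stands too.
- **Site differences.** A reader might assume that discharge or electrolyte care differs by site. Protocol 3.1 gives one set of discharge criteria and one correction protocol for both sites, and no site difference in outcome is reported.

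**Conclusion.** The point holds as one of analysis choice and specification. Analysing two randomisation strata as random clusters is a poor fit: the Aim 1A site variance is close to uninformative, without material bias in the arm contrast. The serious risk is conditional and confined to Aim 1B. If the within-site wording is implemented as a clustered robust variance, the test is invalid, with a rejection rate under the null of 0% (score) or about 40-44% (Wald). If site is simply ignored, type I error is not inflated, and power falls from 71% to 64% only at the largest site effect examined. For Aim 2 the gain from stratifying is small unless event rates differ strongly between sites.

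The one-degree-of-freedom argument and the bound of 2.0 need no trial-specific assumption; the Wald rates depend only on the information split. The power comparisons rest on assumed splits, site effects, medians, censoring and event rates that the documents do not give.

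**What to change.** - **Aim 1A:** enter site as a fixed effect and keep patient as the random effect.
- **Aim 1B:** replace the phrase about within-site correlation with a log-rank test stratified by site; stratify the Cox model by site as well, if it is used.
- **Aim 2 (optional):** use an exact Cochran-Mantel-Haenszel test stratified by site for the incidence comparisons.

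The cost is SAP wording and one degree of freedom, with no new data and no change to sample size. The SAP amendment table records that the randomisation code was broken and the short-term database locked. For the in-hospital outcomes, the sponsor should therefore date the clarification, state which Aim 1B method was used, and give the site-stratified result beside it if that method was different.

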d. Correction of electrolyte abnormalities: Electrolyte abnormalities (serum phosphorus < 3 mg/dL, magnesium ≤ 1.7 mg/dL, or potassium < 3.5 mEq/L) will be corrected with a standardized protocol for both sites. Patients with hypophosphatemia will be treated with sodium potassium phosphate, 250 mg per packet (8 mmol phosphorus, 7.1 mEq potassium), one packet three times a day by mouth for a serum phosphorus between 2.5 and 2.9 mg/dL, two packets (500 mg) three times a day for a serum phosphorus of 2.0 - 2.5 mg/dL, and if serum phosphorus is < 2.0 mg/dL then intravenous sodium potassium phosphorus will be initiated at a dose of 0.24 mmol/kg (max of 15 mmol per dose). The PICU will be contacted and labs will be rechecked STAT 4 hours after the infusion is completed. Those with hypomagnesemia will be prescribed magnesium oxide (150 mg elemental Mg per tablet), one tablet three times a day by mouth for a serum magnesium between 1.3-1.7 mg/dL; two tablets three times a day by mouth for a serum magnesium between 1.0-1.2 mg/dL. In the case of serum magnesium below 1.0 mg/dL, the PICU will be called for possible transfer, and intravenous magnesium sulfate will be started at a dose of 50 mg/kg (max of 2 grams per dose). Labs will be rechecked STAT 2 hours after infusion completed: If repeat serum mag still < 1.0 mg/dL, repeat same dose of magnesium sulfate IV; If repeat serum mag > 1.0, begin PO Mag, at PO dose indicated above. Those with hypokalemia will be prescribed extended release potassium chloride by mouth, 20 mEq for a serum potassium of 3.1-3.4 mmol/L; and 40 mEq for a serum potassium of 2.5-3.0 mmol/L. For a serum potassium between 2.2 - 2.5 mmol/L, 40 mEq extended release potassium chloride will be given STAT and the PICU will be called for possible transfer. Labs will be rechecked in 4 hours (peak) and 12 hours (estimated nadir). For any serum value of potassium < 2.2 mmol/L, intravenous potassium chloride will be initiated and PICU will be called for transfer. Declining electrolyte levels that are in the normal range will not be treated. Participants will also receive a SOC supplement regimen including 500mg elemental calcium with vitamin D twice per day and an adult multivitamin with minerals once per day.

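### No planned Aim 2 comparison distinguishes a mild electrolyte abnormality from one reaching IV correction or PICU contact, so a shift in severity at equal incidence would not show

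*Combined protocol and SAP*

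**What the plan says.** SAP 2.2, Aim 2: "Primary indicator of safety will be incidence of the following electrolyte abnormalities during hospitalization", namely "2A) hypophosphatemia (<3 mg/dL), 2B) hypomagnesaemia (≤ 1.7 mg/dL), 2C) hypokalemia (< 3.5 mEq/L". Each is a yes/no outcome compared by Fisher's exact test. The same sentence that names the test also compares the proportion given corrective supplementation. The next sentence lists that comparison again: "Additional safety outcomes: the proportion receiving electrolyte supplementation during the hospitalization between groups". Neither mention splits by route or level. The remaining comparison is time to electrolyte nadir, by Wilcoxon rank sum test.

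Protocol 3.1.d: "Electrolyte abnormalities (serum phosphorus < 3 mg/dL, magnesium ≤ 1.7 mg/dL, or potassium < 3.5 mEq/L) will be corrected with a standardized protocol". It adds: "Declining electrolyte levels that are in the normal range will not be treated". It then grades the response:

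- **Phosphorus.** Oral packets at milder levels; "if serum phosphorus is < 2.0 mg/dL then intravenous sodium potassium phosphorus will be initiated", followed by "The PICU will be contacted and labs will be rechecked STAT 4 hours after the infusion is completed".
- **Magnesium.** Oral tablets at milder levels; "In the case of serum magnesium below 1.0 mg/dL, the PICU will be called for possible transfer, and intravenous magnesium sulfate will be started".
- **Potassium.** Oral doses at milder levels; an oral dose with a PICU call at 2.2–2.5 mmol/L; IV with a call for PICU transfer below 2.2 mmol/L.

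SAP Section 1 states the Aim 2 hypothesis as no difference in incidence. No margin, sample size or power is given for Aim 2. Appendix Table 2, Amendment 3, says that earlier studies reported rates up to 48% and that monitoring during this trial found very low incidence, without a figure.

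**The concern.** The incidence cut-offs are each electrolyte's own correction-start level, so a participant just under a cut-off and a participant who needs IV correction and a PICU call count the same. The other two comparisons do not recover the difference. Supplementation is any versus none, and time to nadir ignores depth.

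The protocol introduction says that accepted practice relies on lower-calorie refeeding to guarantee safety. This trial tests that belief. Because Aim 2 hypothesises no difference and sets no margin, a non-significant result at the mildest cut-off could easily be reported as evidence of safety. The planned comparisons would give that result even if the severe tier differed between arms. The protocol itself treats the severe tier as important: Appendix Table 1, version 1.1, records that the replacement protocol was extended to more severe levels.

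**Working it through.** The plan states no Aim 2 figure to reproduce. The check is of what each planned comparison can detect, followed by an illustration.

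**1. Can any planned comparison see severity?**

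| Aim 2 comparison | What it records | Changes if oral cases become IV/PICU cases? |
|---|---|---|
| Incidence of each abnormality | Below the correction-start level, yes/no | No |
| Supplementation (listed twice) | Any correction, yes/no | No |
| Time to nadir | Day of the lowest value | Only if timing also changes |

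Protocol 3.1.d corrects values beyond the cut-offs and leaves normal values untreated. Under full adherence, any supplementation and any abnormality therefore pick out essentially the same participants.

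**2. Illustration.** Inputs: 60 per arm (SAP 2.3). The counts are assumed: 12 abnormal in each arm, with 0 in LCR and 6 in HCR reaching IV correction or PICU contact.

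- Incidence, 12/60 v 12/60: Fisher p = 1.00. Supplementation under full adherence: the same table, p = 1.00.
- Severe tier, 0/60 v 6/60: two-sided Fisher p = 2 × C(60,6)/C(120,6) = 2 × 50,063,860/3,652,745,460 = 0.027.
- One event fewer, 0/60 v 5/60: p = 0.057.

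The same pattern holds at other assumed incidences:

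| Abnormal, LCR v HCR | Severe, LCR v HCR | p, incidence | p, severe tier |
|---|---|---|---|
| 29 v 29 | 3 v 12 | 1.00 | 0.025 |
| 18 v 18 | 1 v 8 | 1.00 | 0.032 |
| 9 v 9 | 0 v 6 | 1.00 | 0.027 |

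**3. Would an ordinal test do?** Code none / oral only / IV or PICU. The illustration becomes LCR 48/12/0 and HCR 48/6/6.

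- Midranks: 96 participants at 48.5, 18 at 105.5 and 6 at 117.5. HCR rank sum = 48×48.5 + 6×105.5 + 6×117.5 = 3,666, against 60×121/2 = 3,630 expected. Exact p = 0.81.
- Scores 0/1/2: HCR total = 6×1 + 6×2 = 18, against 15 expected. Exact p = 0.40.

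The large tied group dominates, so an ordinal test misses this shift. The binary severe-tier outcome does not.

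**4. What can a severe-tier test achieve?** Assume equal incidence, with 10% of LCR cases and 50% of HCR cases severe. Fisher power at 60 per arm, by full binomial enumeration:

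| Incidence in both arms | Severe rate, LCR v HCR | Power |
|---|---|---|
| 48% | 4.8% v 24% | 82% |
| 30% | 3% v 15% | 52% |
| 15% | 1.5% v 7.5% | 15% |

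Only the 48% comes from the documents; the other incidences and the severe shares are assumptions. If only 3 HCR participants and no LCR participant were severe, p = 0.24. With no severe event in an arm, the exact two-sided 95% upper limit is 1 − 0.025^(1/60) = 6.0%.

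**The case against.** **Severe events are watched elsewhere.** SAP 2.2 sends these adverse events to the DSMB, IRB and NIH under a monitoring plan that is not in the supplied text and may grade severity. Aim 3 costs adverse events. A reader might infer that severe events could differ wholly unnoticed; the documents do not support that. But neither route is a planned Aim 2 comparison between arms.

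**Supplementation is not simply incidence again.** This is right as far as it goes. A reader might infer that the two are identical by construction, but that needs full adherence. Supplementation is treatment received in an unblinded trial and can reveal departures from 3.1.d. The phosphate packet also carries 7.1 mEq potassium, so the match need not hold for each electrolyte. Even so, it cannot show a change of route.

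**Events will be too few.** This largely stands. With very low incidence, a formal test will rarely reject, and the 0 v 6 example is one chosen split. It is an argument for counts with intervals, not for leaving the tier unreported.

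**It is late and not free.** Also fair. Appendix Table 2, Amendment 1, records that the randomization code was broken (DSMB notified 3 July 2019) and the short-term database locked on 31 July 2019. No section states that PICU contact is captured as data.

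**Conclusion.** The gap is real and follows from the text: no Aim 2 comparison uses nadir depth, IV correction or PICU contact. That supplementation largely repeats incidence assumes adherence to 3.1.d; that no comparison uses severity does not depend on it.

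The size cannot be estimated from the documents, which give neither the observed incidence nor any severe-tier count. The p-values of 1.00 and 0.027 show what the comparisons can and cannot see under assumed counts; they do not predict this trial's result. A reader might infer that HCR caused more severe events, or that the trial hides a harm. Nothing in the documents says so.

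The change is a modest and worthwhile improvement in reporting. It would not turn Aim 2 into a demonstration of equal safety.

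**What to change.** In SAP 2.2, Aim 2, replace the repeated supplementation comparison and keep the other mention. Add:

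1. The number of participants in each arm reaching any IV-correction or PICU-contact tier already defined in Protocol 3.1.d, with exact 95% CIs and Fisher's exact test on that binary outcome. Do not use an ordinal none/oral/IV-or-PICU test.
2. The nadir value of each electrolyte, summarised by arm.
3. A statement that these results are supportive (post hoc if added after the July 2019 unblinding and lock) and that a non-significant result does not show equal safety.

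Two matters come first. Protocol 3.1.d puts potassium 2.5 mmol/L in both the oral-only range (2.5–3.0) and the PICU-call range (2.2–2.5); these must be reconciled before tiers are assigned. Capture of PICU contact must also be confirmed. If it was not captured, use laboratory nadir tier and IV correction.

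**Cost.** SAP wording, plus some record extraction if PICU contact or IV route is not in the database. Daily electrolytes for the first 7 days (3.1.c) and daily supplement intake (3.1.e) are already collected, and consent covers medical record review (2.1.b). The downside is wide intervals and little power.
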